#### **4.1 Inclusion Criteria**

Participants must meet all the inclusion criteria to participate in this study:

- Community residing adults,  $\geq 18$  years
- PLWD defined in one of two ways:
  - A diagnosis using algorithms based on CMS' Chronic Care Warehouse definition of Alzheimer's Disease, Related Dementias, Related Disorders, and Senile Dementia. This definition includes those who have an eligible ICD-9/ICD-10, CPT4, or HCPCS code on any eligible claim (i.e., inpatient, outpatient, SNF, or home health visit or stay) in the past three years or a diagnosis on the patient problem list; OR
  - A dementia medication including donepezil, donepezil/memantine combination, galantamine, rivastigmine, aducanumab, or memantine on the patient medication list or a pharmacy claim in the past three years.
- Actively receiving primary care services at one of three primary care practices within two participating health care organizations selected as study sites.
- Have a reliable care partner who speaks English (or a language spoken by the Memory Care Coordinator).
- Willing to participate in all study home or telephone/video visits and related activities for the entire length of the study (3 months).

#### **4.2 Exclusion Criteria**

All candidates meeting any of the exclusion criteria at baseline will be excluded from study participation:

- PLWD in crisis, e.g., show signs of abuse, neglect, extreme risk of danger to self or others), will be connected to appropriate services, but will be excluded from the study.

#### **4.3 Study Enrollment Procedures**

PLWD will be identified in the EHR of their respective HCOs and approached in two ways. PLWD who present with their care partners for an outpatient office visit will be invited to participate in the program and provided a program information sheet (see Appendix C). After establishing eligibility, dyads can choose to enroll by scheduling an initial home or telephone/video visit with the MCC. Enrollment will begin with an initial needs assessment (the JHDCNA, Appendix B) during a home or telephone/video visit. Telephone intake will be supplemented with a home visit at a later date or photos of the living situation to identify safety issues or ways to improve the PLWD's care. Sites will also identify PLWD in the EHR who meet program eligibility criteria but are not scheduled for a visit. To ensure equity, racial minorities and other underserved populations will be prioritized and approached using culturally sensitive processes to ensure a representative sample of participants. Care partners/PLWD will be contacted by telephone to enroll in the program using a script, based on local context and cultural adaptation of an existing script (see Appendix D). Recruitment will be supported with existing MIND outreach and engagement resources. To assess feasibility and validity of eligible patient identification, referral, and enrollment, MCCs will electronically record the number of patients flagged as eligible, referred, enrolled, and retained or who refused, were unreachable, or lost to follow-up. Referral, recruitment, patient acceptance, and attrition rates will be calculated to assess the feasibility of use of the algorithm and of the

recruitment protocol. MCCs will enroll a minimum of seven PLWD every other week for a maximum caseload of 42, to accommodate other non-dementia patients who may be part of the MCC total caseload.

As this is a minimal risk, best-practice based quality improvement intervention, a waiver of consent will be requested for this study for both the intervention patients and the data validation arm cohort. Further justification is described in section 11.2.

Patients will not be randomized for this pilot study.

## **5 STUDY INTERVENTIONS**

### **5.1 Interventions, Administration, and Duration**

We will embed and implement an evidence-based dementia care coordination model, MIND at Home, at three primary care practice sites. The five key Program Components include: (1) identification of dementia-related needs for the PLWD and care partner, using standardized procedures and definitions, including an in-home or telephone/video assessment supplemented by photos of the home by the MCC using the JHDCNA (13 domains, 61 items); (2) family-centered need-based care planning involving MCC in collaboration with the PC team, following standard protocol provided the MCC and staff, to address unmet needs and match priorities/preferences of the PLWD and family targeting both medical and non-medical determinants of health relevant for all stages of dementia (including social and environmental needs); (3) implementation of care plans linked with proven practice derived care strategies/interventions (e.g., education, coaching, symptom/need assessment, referrals, care coordination/navigation) by the MCC using standardized proven methods and need-based protocols; (4) care monitoring and plan revision, which include regular contact at least every 30 days; and (5) standardized initial program orientation for all PC team members and MCCs and weekly virtual collaborative learning sessions that include a structured case discussion (de-identified) and a short didactic on a specific care topic. Sessions are attended by geriatric psychiatry to support the PC care team's work and advance dementia assessment and care management capacity at PC sites.

**MIND Program Bundle:** Existing materials will be utilized for this pilot that include, but are not limited to: staff orientation and onboarding materials (e.g., web-based certifications, scope of practice (SOP) manual, role definitions, and job descriptions, etc.); intervention protocol (MIND at Home Intervention Handbook©, MIND Intervention Field Reference Guide© (Appendix A), Care Plan Builder Template,© Telecollaborative Toolkit© and the JHDCNA [Appendix B]); and enrollee support, engagement and resources (outreach and program promotion materials, Caregiver Resource Toolkit). Select tools are included as Appendix A and B.

**Program delivery:** Enrolled patients will receive office- plus home- or telephone/video-based initial care needs assessment using the JHDCNA including (but not limited to) safe medication administration and adherence; nutrition and hydration; home safety issues (e.g., environmental hazards, wander- and fall-risk management); daily routine and meaningful activities; advanced care planning; and 18 items addressing care partner needs. Telephone needs assessments will be supplemented with photos/videos of the home environment. Following the needs assessment, the MCC will develop a care plan in collaboration with the PLWD's PCP and other team members. MCCs will then review the care plan with the PLWD/care partner, prioritize needs, and provide a written copy to the PLWD/care partner that identifies specific need items and individualized recommendations for linked care strategies/interventions. The MCC, supported by the PCP and an interdisciplinary team, will then work with the PLWD and care partner to prioritize and address identified needs. PLWD may select the interventions/treatments they or their PCP deem appropriate (absolute adherence to recommendations is not required). Enrollees will have a minimum of three contacts over three months (e.g., mix of phone/video and in-home visits) but contact

intensity will be driven by individual needs and preferences. Participating dyads will have regular access to their MCC through phone, video conference, text, email, and the EHR patient portal. In addition to the written care plan, participating care partners will also receive the MIND Caregiver Resource Toolkit, a hardcopy binder with select tools and individualized resources.

**Team orientation and support:** MCCs, who have already been identified by each HCO, will initially complete an eight-module, interactive online MIND certification course (15 CME/CEU), during which they will learn skills specific to the care of PLWD as well as program processes. Delivery of the intervention involves orientation to the MIND program tools (discussed above). The online orientation will be followed by two virtual, half-day practice- and scenario-based learning sessions with the JHU lead investigator ([name]) and the JHU geriatric psychiatrist ([name]), during which the MCCs can ask questions about the information in the orientation modules and the practice elements of assessment and care planning protocols. During orientation and in close collaboration with the MCC and PC care team, the JHU team will help adapt the program resources and tools to the local setting/team to accommodate the diverse needs and cultures of the populations being served. Throughout the pilot study period, the MCC and Study Site Leaders will meet every other week with the AMGA/JHU research team, as well as PRN with the JHU MIND team (geriatric psychiatrist, Senior MCC, lead investigator). The MCCs will be expected, and PC care team will be strongly encouraged, to attend weekly virtual collaborative case conferences and clinical sessions with the JHU MIND faculty clinical support team (1 CME/CEU/session). These activities are designed to promote co-learning and mentorship, review new cases, and discuss ongoing complex cases.

## 5.2 Handling of Study Interventions

The delivery of this behavioral intervention is described in the previous section.

## 5.3 Concomitant Interventions – N/A

## 5.4 Adherence Assessment

Implementation feasibility will be assessed by collecting a standard set of process measures and fidelity metrics. For all participant dyads, process measures will be collected by the MCC and submitted monthly to the AMGA research analyst including number, duration, type, and general content of encounters per dyad to assess the feasibility of implementation within PC practices. All process measures will be monitored and stratified by using socio-demographic data on participants (rurality, race/ethnicity) to assess differential rates of adherence, attrition/retention. Fidelity will be assessed by tracking completion of core intervention components (# needs assessment completed, # care plans completed, # completed 3 months, # with MCC encounter at least once every 3 months), and attendance at weekly virtual learning sessions by team member types (>50% of sessions). Collection of this information is facilitated by documents created for MIND on program implementation fidelity. See Appendix A. Fidelity measures will be captured and monitored using a work process template/spreadsheet completed by MCCs for each assigned dyad for each encounter. The template serves as an operations checklist the MCC completes at each home or telephone/video visit/contact that includes each component of the visit, the care plan with needs being addressed, actions taken, and follow up plans. A de-identified version of the management template will be shared with the JHU Investigators (Drs. [name] & [name]) biweekly for review and feedback. De-identified program implementation data will be sent by the study site to the AMGA research analyst weekly. The MCC will contact the care partner to assess whether the care plan recommendations have been implemented.

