#### Design and Outcomes

Using a pragmatic trial design, *this project will embed and test the feasibility of a novel best practice-based approach*, MIND at Home, within PC to enhance and elevate the role of existing PC staff to Memory Care Coordinators (MCCs), increase PC access to interdisciplinary collaborative care, and systematically combines the benefits of clinic-based services with home- or telephone/video-based assessment to support family-centered care planning and implementation for PLWD and their care partners. Weekly virtual collaborative learning sessions that include geriatric psychiatry consultants augment the PC care team's work to support the development and mastery of, and confidence in, dementia assessment and care management skills at the PC sites. Our *overarching goal* is to test and establish feasibility, acceptability, fidelity, and sample size/referral rate data for MIND at Home in PC to prepare for a future multi-site embedded pragmatic trial.

- Aim 1: Evaluate the feasibility and validity of eligible PLWD identification, referral, and enrollment in a best practice-based dementia care coordination program (MIND at Home) at 3 primary care clinics.
- Aim 2: Evaluate the feasibility, acceptability, and fidelity of implementing MIND at Home in 3 primary care clinics in 2 geographically and demographically diverse integrated health systems.
- Aim 3: Evaluate the feasibility of ascertainment of patient-level outcomes over time using electronic health record (EHR) data.

Embedding a collaborative, best-practice based approach such as MIND at Home into PC is a potentially powerful strategy to organize care, improve quality, reduce costs, and maximize population-level benefit for PLWD. This proposal tests the feasibility of implementing MIND at Home into PC in a racially, ethnically, and geographically diverse PLWD population to prepare for a multisite ePCT to evaluate effectiveness, and eventually to support broader dissemination and uptake in PC.

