#### Interventions and Duration

This study will test a single intervention. **Maximizing Independence at Home–MIND at Home (MIND)** is a comprehensive care coordination program born from geriatric psychiatry. This model takes an interdisciplinary, collaborative care approach to care by systematically assessing and addressing a wide range of dementia-care related needs of both PLWD and their care partners that place both at increased

risk for poor outcomes.

The five key program components include: (1) identification of dementia-related needs for the PLWD and care partner, using standardized procedures and definitions, including an in-home or telephone/video assessment by the MCC using the Johns Hopkins Dementia Care Needs Assessment (JHDCNA) (13 domains, 61 items; see [Appendix B](#)); (2) family-centered need-based care planning involving the MCC in collaboration with the PC team, following standard protocol, to address unmet needs and match priorities/preferences of the PLWD and family targeting both medical and non-medical determinants of health relevant for all stages of dementia (including social and environmental needs); (3) implementation of care plans linked with proven practice derived care strategies/interventions (e.g., education, coaching, symptom/need assessment, referrals, care coordination/navigation) by the MCC using standardized proven methods and need-based protocols; (4) care monitoring and plan revision, which include regular contact at least every 30 days; and (5) standardized initial program orientation for MCCs and all PC team members and weekly virtual collaborative learning sessions that include a structured case discussion (de-identified) and a short didactic on a specific care topic. Sessions are attended by geriatric psychiatry to support the PC care team's work and advance dementia assessment and care management capacity at PC sites.

PLWD and their care partners will be enrolled for a total of 3 months.

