### **Sample Size and Population**

Using a pragmatic trial design, 150 community-residing PC PLWD will be enrolled in the program, each for a 3-month period. Data on an additional 100 PLWD will be pulled for validation purposes.

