#### Screening by Clinic Staff

PLWD will be identified in the EHR of their respective HCOs, by clinic staff, as ever having a diagnosis of ADRD or prescription for a dementia-related medication, on an administrative claim, patient problem list (Dx), or patient medication list (Rx) for the duration of time the patient has data in the EHR. Patients with an existing diagnosis of mild cognitive impairment may be assessed for ADRD during the visit by their provider. Patients must be living at home and in the care of an informal care partner. Patients eligible for the study based on EHR data will be flagged prior to their visit. Once the provider has confirmed eligibility by confirming diagnosis or medication and living situation, eligible PLWDs and their care partners will be invited to participate in the program. For PLWD without a scheduled visit, care partners/PLWD will be contacted by telephone to enroll in the program using a script, based on local context and cultural adaptation of an existing script. (See Appendix D.)

After establishing eligibility, enrollment will be initiated by scheduling an initial home, telephone, or video visit with the MCC. Enrollment will begin with a needs assessment (JHDCNA) during the intake visit.

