### 6.2.3 Follow-up Visits

Enrollees will have a minimum of three contacts with the MCC over three months (e.g., mix of phone and in-home visits). Contact intensity will be driven by individual needs and preferences.

There are no required office visits during the intervention.

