**Program implementation feasibility (Aim 2).** Implementation feasibility will be assessed by collecting a standard set of process measures and fidelity metrics. For all participant dyads, process measures will be collected by the MCC and submitted monthly to the AMGA research analyst including number, duration, type, and general content of encounters per dyad will be calculated to assess the feasibility of implementation. All process measures will be monitored and stratified by minority participants (rurality, race/ethnicity) to assess differential rates of adherence, attrition/retention. Fidelity will be assessed by tracking completion of core intervention components (# needs assessment completed, # care plans completed, # completed 3 months, # with MCC encounter at least every 3 months), and attendance at weekly virtual learning sessions by team member types (>50% of sessions). Collection of this information is facilitated by documents created for MIND on program implementation fidelity. (See [Appendix A](#).) Fidelity measures will be captured and monitored using a work process template/spreadsheet completed by MCCs for each assigned dyad for each encounter. The template serves as an operations checklist the MCC completes at each home visit/contact that includes each component of the home, telephone, or video visit, the care plan with needs being addressed, actions taken, and follow up plans. All data collected on participants will be collected electronically, encrypted during upload, download, and transfer, using password-protected files, and saved on password-protected computers.

A de-identified version of the management template will be shared with the co-investigators (Drs. [name] & [name]) biweekly (i.e., every other week) for review and feedback. De-identified program implementation data will be sent by the study site to the AMGA research analyst monthly. Acceptability will be assessed from multiple stakeholder perspectives. In the final 2 months of the pilot, brief surveys developed in prior MIND studies will be sent (email or mail) to dyads (post program) to assess experience (satisfaction, perceived benefit, challenges, ways to improve program). The participant survey is included in the Appendix.

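### The contact fidelity item asks for one MCC encounter in the whole 3-month program, while the intervention is defined by contact every 30 days and at least three contacts

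*Combined protocol and SAP*

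**What the plan says.** **Intervention definition.** The Précis (Interventions and Duration) lists as the fourth key component "care monitoring and plan revision, which include regular contact at least every 30 days". Section 5.1 repeats this.

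**Minimum number of contacts.** Section 5.1, under program delivery: "Enrollees will have a minimum of three contacts over three months". Section 6.2.3: "Enrollees will have a minimum of three contacts with the MCC over three months". Both add that intensity above this floor follows need and preference.

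**Length of enrollment.** The Précis (Sample Size and Population) enrolls 150 people living with dementia, "each for a 3-month period".

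**Fidelity measures.** Section 5.4 lists counts of needs assessments completed, care plans completed, dyads completing three months, and dyads "with MCC encounter at least once every 3 months", plus attendance at the learning sessions. Section 10.1 (Aim 2) gives the same list, with the contact item as "with MCC encounter at least every 3 months".

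**Related data.** Sections 5.4 and 10.1 also have the MCC submit process measures monthly, including the number and duration of encounters for each dyad, and complete a template for each encounter. Section 9.5 says that fidelity data and process measures will both be reported.

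**Use.** Aim 2 is to "Evaluate the feasibility, acceptability, and fidelity of implementing MIND at Home in 3 primary care clinics". Section 7.7 puts fidelity, judged by how complete the intervention components are, into the data and safety monitoring report.

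**The concern.** A fidelity item should separate participants who received a component as defined from those who did not. Here the component is defined by 30-day contact with at least three contacts, but the item is passed with a single encounter in the whole enrollment. Because it appears in two sections with nearly the same wording, it is unlikely to be a slip in one place.

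At stake is what the pilot reports. Whether primary care staff can sustain the program's contact schedule is one of the things Aim 2 is meant to find out. A contact figure near 100% could go into the results, the monitoring report and the planning of the full trial, although the schedule had not been kept.

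**Working it through.** The plan states no figure to reproduce. The check compares thresholds.

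**1. Encounters required in one enrollment**

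| Rule | Source | Required, taking 3 months as 90 days |
|---|---|---|
| Contact fidelity item | Sections 5.4, 10.1 | 90 / 90 = 1 |
| Contact at least every 30 days | Précis, Section 5.1 | 90 / 30 = 3 |
| Minimum number of contacts | Sections 5.1, 6.2.3 | 3 |

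The item is set at one third of the plan's own minimum. A dyad with one or two contacts falls below the minimum and passes the item.

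**2. Does intake count?** The documents do not say.

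- *Intake counts.* Section 6.2.1 says "Enrollment will begin with a needs assessment (JHDCNA) during the intake visit", the Précis has the MCC do that assessment, and Section 5.4 has the template completed at each visit or contact. This is the natural reading. Every dyad with an intake then passes with no follow-up (0 follow-up contacts for the item, 2 for the three-contact minimum).
- *Intake is excluded.* This is possible because completed needs assessments are counted separately. The item then fails only a dyad with no follow-up at all (1 follow-up contact for the item, 3 for the minimum).

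Treated the same way in both rules, the gap is 2 contacts per dyad: 2 − 0 or 3 − 1.

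**3. The two standards are not interchangeable.** Three contacts in the first month and none later meet the three-contact minimum but not the 30-day rule. Conversely, in a 90-day enrollment, follow-up contacts on days 30 and 60 after intake leave no gap above 30 days, but they make only two contacts if intake is excluded from the minimum.

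**4. Illustration under an assumption.** Suppose intake is excluded, each dyad has at most one contact per month, and contact occurs in each of the three months independently with probability q. The documents give no q. Then P(passes item) = 1 − (1 − q)³ and P(reaches three contacts) = q³.

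| Assumed q | Passes item | Reaches three contacts |
|---|---|---|
| 0.5 | 1 − 0.125 = 87.5% | 12.5% |
| 0.7 | 1 − 0.027 = 97.3% | 34.3% |
| 0.9 | 1 − 0.001 = 99.9% | 72.9% |

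These values show how weakly the item responds to the level of contact. They do not forecast delivery, and the finding does not depend on them.

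**5. Could the existing records supply the missing check?** Encounter numbers per dyad give the three-contact count directly. Monthly counts show whether contact occurred in each month but not the spacing: with 30-day months, contacts on day 1 and day 60 fall in consecutive months and are 60 − 1 = 59 days apart. Checking the 30-day rule needs the timing of encounters, which the per-encounter template may already hold.

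**The case against.** The strongest reply is that a shortfall need not stay hidden. Encounter numbers per dyad are submitted monthly, are to be stratified by rurality and by race and ethnicity (Section 5.4), and are to be reported with the fidelity data (Section 9.5). De-identified templates are reviewed every other week (Sections 5.4 and 10.1; Section 10.3.5 limits this to the first three months). What is missing is a threshold applied to data already in hand.

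The other fidelity counts also cover part of the ground. The care plan is to be reviewed with the dyad (Section 5.1), and a final MCC visit is planned in Study Month 3 (Section 6.2.4). If the counts of completed care plans and completed three months follow those descriptions, intake, plan review and final visit make about three contacts. Appendix A, which Section 5.4 cites for fidelity documents, was not available and may hold a contact metric.

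Most of this stands, and it limits the consequence. It does not remove the point: the process measures carry no contact threshold, completion is not defined, none of these counts tests 30-day spacing, and Sections 5.4 and 10.1 would still state a different interval whatever Appendix A contains.

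Three stronger readings are tempting:

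- *That the plan cannot detect low contact.* The process measures may show it, and with intake excluded the item does flag a total absence of follow-up.
- *That dyads will be contacted too little.* The documents give no delivery rate and do require the contacts.
- *That the two-contact gap can be multiplied by 150 dyads to give contacts lost.* That would place every dyad at the item's minimum, which nothing supports.

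**Conclusion.** The item is wrong as written. It requires one encounter where the plan's own minimum is three, and it does not test 30-day spacing. It is close to automatic if intake counts, and it flags only zero follow-up if intake does not. The contact fidelity figure for Aim 2 and for the monitoring report could therefore look complete when contact was below the plan's standard, although other reported data may reveal this.

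The severity is minor to moderate. No stated progression rule, clinical outcome or safety action depends on the item, and the pilot tests no hypothesis (Section 9.1). The mismatch between sections is certain. That no fidelity measure applies the 30-day or three-contact standard is established only for the visible text, without Appendix A.

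**What to change.** 1. Reconcile the contact item in Sections 5.4 and 10.1 with the Précis and Sections 5.1 and 6.2.3. Which interval stands is for the study team.
2. Score the contact fidelity item against that standard, and state whether intake counts as an encounter.
3. While the current text stands, report from the existing templates and monthly counts (a) the number and percent of dyads meeting the 30-day standard, with its operational definition, and (b) separately, the number and percent with at least three contacts.
4. Only if the existing records do not allow the spacing check, add one template field for days since intake. This fits Section 11.3.1.1, which avoids exact dates.

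The cost is a few lines of wording and at most one template field, with no added contact with participants. The reported fidelity figure may be lower than under the current item.
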